Baseline	Information and values collected during Screening. The RA disease activity assessments that serve as the baseline assessments used for determination of the primary and key secondary efficacy endpoints must be performed on the day of informed consent.
CDAI	
The CDAI score is based on 4 items:
 
 • TJC28 • SJC28

Term	Definition
	
 SGA EGA 
The CDAI score is calculated as follows and ranges from 0 to 76:
 
 CDAI = TJC28 + SJC28 + SGA + EGA 
The CDAI score corresponds to the current RA activity:
 
 0 to \leq 2.8 Remission >2.8 to \leq 10 Low disease activity (LDA) >10 to \leq 22 Moderate disease activity > 22 High disease activity 
The MCID is a score reduction by 12 if starting in high activity, 6 if starting in moderate activity, and 1 if starting in low activity.

Control to Open Label (COL) population	Control subjects from ITT population who received non-active (sham) stimulation through Week 12, switched to active stimulation after completing Week 12 assessments, continued to receive active stimulation during open-label follow-up, and for whom follow-up data are available.
Crossover	The process of switching from an initially assigned treatment to the other treatment being studied.
DAS28-CRP	
The DAS28-CRP score is a composite index providing a measure of disease activity, comprising:
 
 TJC28 SJC28 SGA hsCRP (mg/L) 
A total score ranges from 0 to 10 and is computed as follows:
 $\text{DAS28-CRP} = 0.56 * \text{sqrt}(\text{TJC28}) + 0.28 * \text{sqrt}(\text{SJC28}) + 0.36 * \ln(\text{CRP}+1) + 0.014 * \text{SGA} + 0.96$ 
The DAS28-CRP score corresponds to the current RA activity:
 
 0 to $<$ 2.6 Remission 2.6 to $<$ 3.2 LDA 3.2 to \leq 5.1 Moderate activity > 5.1 High activity 
A DAS28-CRP score reduction by 1.2 represents the MCID.

Day 0 (randomization, initiation of stimulation)	
Scheduled study visit occurring 14 to 21 days after Implant Procedure during which subjects undergo the following study procedures in the order specified:
 
 Day 0 assessments Randomization Initiation of stimulation 
Subjects must receive final surgical clearance with an approval to initiate study treatment before proceeding to the Day 0 visit.

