10.2 Exclusion Criteria

Subjects eligible for enrollment in the study must meet *none* of the following exclusion criteria:

1. Have taken biologic or targeted synthetic DMARDs within the minimum required number of washout days prior to Implant Procedure (see **Appendix A**)
2. Demonstrated an inadequate response or loss of response to JAKi, once 6 subjects meeting this criterion have been enrolled.
3. Have received an intra-articular corticosteroid injection within 30 days of Implant Procedure
4. Are currently receiving glucocorticoids at doses greater than 10 mg QD of prednisone (or equivalent) or have been receiving an unstable dosing regimen within 14 days of informed consent
5. Have started treatment with NSAIDs or have been receiving an unstable dosing regimen of NSAIDs within 14 days of informed consent. Over-the-counter use of NSAIDs is permissible (see Section 14.3)
6. Regular use of or dependency on nicotine products within the past 2 years, including but not limited to cigarettes or other nicotine-containing products such as cigars, pipe tobacco, chewing tobacco, patches, gums, lozenges, or electronic cigarettes. Subject does not agree to abstain from using nicotine-containing products throughout study participation.
7. Woman who is either pregnant or breast feeding
8. Woman of childbearing potential who does not agree to use an effective method of contraception. If a woman becomes or decides she wants to become pregnant, the implant must be decommissioned and the subject followed for safety, per standard of care.
9. Untreated or poorly controlled psychiatric illness or history of substance abuse
10. Active infection requiring treatment with antibiotics or corticosteroids at Screening, unless cleared before Implant Procedure
11. Significant immunodeficiency due to underlying illness (e.g., active, untreated HBV/HCV and HIV positive)
12. History of CVA or transient ischemic attack, or diagnosis of cerebrovascular fibromuscular dysplasia
13. Clinically significant cardiovascular disease, including cardiomyopathy with ejection fraction < 40%, myocardial infarction, unstable angina, or diagnosis of congestive heart failure (NYHA Class III or IV) in the preceding 12 months. Subjects with current, clinically significant cardiovascular disease must obtain clearance from a cardiologist prior to the implant procedure
14. Neurological syndromes including multiple sclerosis, Alzheimer's disease, or Parkinson's disease

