11.2 Informed Consent and Screening

11.2.1 Informed consent

If the patient appears to be a potential candidate for the study based upon existing information, a written informed consent will be obtained. Informed consent must be obtained prior to initiation of any clinical procedures that are performed solely for the purpose of determining eligibility for research, including withdrawal from medication. Patients who have completed or are in process of washout unrelated to this study may be considered for the study. When washout is done solely in anticipation of or in preparation for the research, it is part of the research and must be done after obtaining written consent.

Clinical investigators or designees will approach the patient to obtain a written informed consent. The background of the proposed study, the implant procedure, the follow-up schedule and all potential risks and benefits will be carefully explained to each patient. The clinical investigator or designee obtaining informed consent shall:

- Avoid any coercion of or undue influence of patients to participate,
- Not waive or appear to waive patient's legal rights,
- Use language that is non-technical and understandable to the patient, and
- Provide ample time for the patient to consider participation.

Each patient must sign and date the ICF approved by an appropriate IRB during an in-office visit. The original signed ICF will be placed in the study file, and a copy will be given to the subject.

Subjects will be re-consented in situations where changes were made to the study protocol or new information about the risks, possible benefits or alternative treatments have been identified. The sponsor and IRB will notify clinical investigators in the event re-consent is necessary. In this case, subjects must sign and date the amended ICF during their next in-office visit. The original will be placed in the study file, and a copy will be given to the subject.

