11.2.2 Screening and baseline assessments

During the same in-office visit that written informed consent is obtained, each subject will be assigned a unique identifying code and undergo the following screening assessments to confirm their initial eligibility and obtain baseline values for RA disease activity assessments from which the primary and the key secondary efficacy endpoints will be assessed:

- Physical examination, including vital signs, height and weight

Note: If a subject has an active infection that does not clear before Implant Procedure, the subject is considered as a screen failure. The subject can be consented and screened following treatment and full recovery.

- Prior and current RA medications with detailed record of use of biologic, conventional and targeted synthetic DMARDs
- Medical history
- Female subjects of childbearing potential must confirm their nursing status, undergo pregnancy test, and confirm their birth control method(s) (see Section 12.1)
- RA disease activity assessments (see Section 12.2)
- Determining the need for washout from biologic or targeted synthetic DMARDs prior to Implant Procedure, depending on subject's current usage:
 - *Subjects in post-washout, requiring no further washout.* Subjects who stopped taking all biologic and targeted synthetic DMARDs for a period exceeding the required minimum washout period prior to Implant Procedure (see **Appendix A**) do not require further washout to qualify for the study.
 - *Subjects during washout, requiring completion of washout.* Subjects who stopped taking any biologic and targeted synthetic DMARDs within less than the required minimum washout period prior to Implant Procedure (see **Appendix A**) must complete washout during the screening period, prior to Implant Procedure to qualify for the study.
 - *Subjects in pre-washout, requiring washout.* Subjects who are currently taking any biologic and/or targeted synthetic DMARDs must stop taking them for the required minimum washout period during the screening period, prior to Implant Procedure (see **Appendix A**) to qualify for the study.

Note: If the required minimum washout period following informed consent exceeds 30 days for a given subject, this subject shall be considered screen failure without the possibility of reconsenting. This is because washout needs to be completed before Implant Procedure, which takes place within 30 days from the informed consent date.

- Energizer fit test
- Eligibility evaluation

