11.3 Enrollment and Implant Procedure

Subjects meeting final eligibility criteria and in whom the implant procedure is attempted are considered enrolled. The implant procedure shall occur within 30 days from informed consent. The implant procedure is an outpatient procedure taking place in an operating room under general anesthesia. The implant (MicroRegulator) and POD will be placed on the left cervical vagus nerve within the carotid sheath by surgeons trained and experienced in procedures involving implantation of VNS devices. The implant procedure must be performed according to SetPoint System Instructions for Use Surgeon Manual. All surgeons performing the implant procedure must have documented training prior to performing the first case. Upon completing the implant procedure, any AEs, device deficiencies and changes in concomitant medications will be recorded.

The pregnancy testing for female subjects of childbearing potential must be completed before initiation of the implant procedure (see Section **12.1**).

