14.3 Allowed Medications

The following medications are allowed during study participation:

- Glucocorticoids at the equivalent of \leq 10 mg prednisone daily may be continued at a dose documented to have been stable within 14 days prior to informed consent and until Week 12.
- NSAIDs: over the counter may be continued and those by prescription listed below at the approved dose for RA documented to have been stable within 14 days prior to informed consent and until Week 12:
 - Celecoxib (Celebrex)
 - Diclofenac (Voltaren, Cataflam)
 - Diflunisal (Dolobid)
 - Etodolac (Lodine)
 - Flurbiprofen (Ansaid)
 - Ibuprofen (Motrin)
 - Indomethacin (Indocin)
 - Ketoprofen (Orudis, Oruvail)
 - Ketorolac (Toradol)
 - Meloxicam (Mobic)
 - Nabumetone (Relafen)
 - Naproxen (Anaprox, Naprelan, Naprosyn)
 - Piroxicam (Feldene)
- Mild oral opiates (i.e., acetaminophen-codeine [Tylenol 1, 2, 3], tramadol [Ultram], pentazocine [Talwin], hydrocodone [Vicodin, Lortab]) taken as needed to treat pain. Must not be taken 24 hours prior to RA disease activity assessments.

Note: Mild oral opiates taken on a regular basis to treat pain may be continued at a dose documented to have been stable within 14 days prior to informed consent.

Initiating or changing any of the above listed glucocorticoids, NSAIDs or oral opiates after study entry and until completion of Week 12 assessments is not allowed. Any change must be noted on the Concomitant Medication Log.

Temporary, perioperative changes to any of the above listed medication is allowed at the discretion of the Co-PI Surgeon to reduce the risk of potential bleeding, infection, delayed wound healing, or post-operative pain related to the implant procedure. Such changes are considered standard of care and shall be noted on the Concomitant Medication Log.

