5.8.1 Missing data for efficacy and safety endpoints

Missing data for each efficacy endpoint will be handled as described in Sections 8.2, 8.3, 8.4 and 8.6.

For continuous endpoints, change from baseline will be set to missing at visits with missing post-baseline values or where data were imputed to missing. Continuous efficacy endpoints will be set to missing for subjects who received rescue treatment before Week 12.

For binary endpoints, subjects with missing efficacy data, early withdrawals, or subjects who received rescue treatment before Week 12 will be imputed as non-responders and therefore treated as a failure (e.g., no ACR20/50/70 response, DAS28-CRP remission or no moderate/good EULAR response).

Additional rules for handling of missing data and rescue treatments are detailed below:

- *Missing efficacy data.* Visits with missing data (due to a missed visit or missing component of a composite endpoint) will be set to treatment failure.
- *Early withdrawals.* Only visits following the early withdrawal visit will be set to treatment failure.
- *Prednisone equivalent >10 mg/day.* The visit after a period (time from previous visit up to the day before the current visit) of average daily corticosteroid use exceeding 10 mg/day prednisone will be set to treatment failure and continuous endpoints set to missing due to rescue.
- *Corticosteroid injection.* If subject received a corticosteroid injection within 30 days prior to a study visit, that visit will be set to treatment failure and continuous endpoints set to missing due to rescue.
- *b/ts/csDMARD.* Subjects who receive treatment before Week 12 with biologic, targeted synthetic, or additional conventional synthetic DMARD, or increased dose of background

conventional synthetic DMARD will be set to treatment failure at all subsequent visits and continuous endpoints set to missing due to rescue.

- *Missing baseline value.* For efficacy endpoints, a missing value at baseline will not be imputed, and the endpoint will be set to missing for all visits.
- *Missing analytes/ retests.* If an analyte value is missing/its concentration cannot be reliably determined (e.g., sample was lost, damaged, etc.), a retest value will be used for that analyte. If an initial value is non-missing and reliable but the analyte was retested, the value that coincides with the date of clinical assessment will be used. If neither an initial nor retest value is available, the analyte value will be set to missing.

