8.3.1 Definition

A subject achieves ACR20 response when this subject experiences a $\geq 20\%$ improvement from baseline on the day of informed consent to Week 12 in TJC28, SJC28, and at least 3 of the following 5 items:

- Subject's pain assessment
- SGA
- EGA
- HAQ-DI
- hsCRP

For all visits, if any of the component scores are missing, then those scores will be considered as not having met the criteria for improvement. If 3 or more of the 5 remaining ACR measures are missing, ACR20 will each be considered as "no response" in the final dataset.

For component scores with missing baseline values or a baseline value of 0, the percentage improvement cannot be calculated, and the component will be considered as not having met the criteria for improvement for all visits.

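### The 30-day steroid-injection exclusion counts back from the implant, not from the consent-day baseline of the primary ACR20, and the 24-hour opiate rule cannot be required before that baseline

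*Protocol*

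**What the plan says.** **Baseline.** Protocol section 3 says that the assessments used for the primary and "key secondary efficacy endpoints must be performed on the day of informed consent". Protocol 11.2.2 places them accordingly: "During the same in-office visit that written informed consent is obtained". SAP 8.3.1 defines the primary response as "improvement from baseline on the day of informed consent to Week 12 in TJC28, SJC28" and in at least three of five further items.

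**Implant date.** Protocol 11.3: "The implant procedure shall occur within 30 days from informed consent".

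**Injections.** Protocol 10.2, exclusion 3, bars those who "Have received an intra-articular corticosteroid injection within 30 days of Implant Procedure". Protocol 12.2.4 makes a joint unevaluable if it is injected in the course of the study. Protocol 14.4 prohibits injections through the Week 12 assessments and states no look-back before consent. SAP 5.8.1 adds, for visits: "If subject received a corticosteroid injection within 30 days prior to a study visit, that visit will be set to treatment failure".

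**As-needed opiates.** Protocol 14.3: "Must not be taken 24 hours prior to RA disease activity assessments". The protocol summary says the same in general terms. Protocol 11.2.1 requires consent before any procedures "performed solely for the purpose of determining eligibility for research, including withdrawal from medication".

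**The concern.** The look-back in exclusion 3 and the primary baseline have different reference dates, which can lie up to 30 days apart. A subject injected shortly before consent can be eligible and contribute a baseline lowered by the injection, which is then compared with a Week 12 value taken without one. ACR20 is a percentage improvement, so a lowered baseline raises the real improvement needed for response in joint counts and possibly in pain, global assessments and HAQ-DI.

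The opiate rule raises a related problem. The hold can be required before Day 0 and Weeks 4, 8 and 12. At the consent visit the subject has not yet agreed to anything, and the protocol does not allow withdrawal of medication for research before consent.

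At stake are the response rates in both arms, the difference between them, and the power of the primary test.

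**Working it through.** **1. Injection-free days before consent.** Inputs: the 30-day look-back from implant (exclusion 3) and an implant k days after consent, k from 0 to 30 (11.3). Days before consent that are covered = 30 - k.

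| k (days) | 0 | 7 | 14 | 21 | 28 | 30 |
|---|---|---|---|---|---|---|
| covered days | 30 | 23 | 16 | 9 | 2 | 0 |

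Example: an injection one day before consent with implant on day 30 is 31 days before implant, so the subject is not excluded.

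**2. Does another rule close the gap?** Protocol 12.2.4 reaches only joints injected during the study. Protocol 14.4 has no pre-consent look-back. SAP 5.8.1 turns an affected visit into a treatment failure but places no condition on the baseline value. Exclusions 4 and 5 (oral glucocorticoids and NSAIDs) count from consent but do not address injections. The gap stays open.

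**3. Effect on one subject (illustrative values).** The ACR20 joint-count target is a count at or below 0.8 x baseline.
- True tender joint count 8: 6.4, so 6 or fewer (25% real improvement).
- Measured as 7: 5.6, so 5 or fewer (3/8 = 37.5%).
- Measured as 6: 4.8, so 4 or fewer (4/8 = 50%).

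Likewise, pain of 7 needs 5 or less (0.8 x 7 = 5.6); the same pain recorded as 5 needs 4 or less.

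**4. Opiates.** Set side by side, 14.3 applies to every RA disease activity assessment without exception, 11.2.2 puts the first one at the consent visit, and 11.2.1 bars research-only withdrawal before consent. The rule therefore covers the visit, but the site has no authority to require it. No eligibility criterion on recent as-needed use stands behind it, and 11.2.2 lets concomitant medications be recorded after the consent day.

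**5. The plan's power.** Exact enumeration with 30 then 95 per arm, stopping if the Stage 1 difference is below 10 points, and a pooled chi-square test at one-sided 0.025:

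| Rates | Stop, computed (stated) | Power, computed (stated) |
|---|---|---|
| 60% vs 30% | 0.040 (0.040) | 0.959 (0.959) |
| 50% vs 30% | 0.173 (0.173) | 0.774 (0.773) |

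The plan's figures reproduce.

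**6. Power under dilution (assumed inputs).** Let a fraction f of each arm have a suppressed baseline and let their chance of response be cut by c. Both rates are multiplied by 1 - f x c.
- f = 5%, c = 1/3: factor 0.983. Rates 59.0% vs 29.5% give power 0.955; 49.2% vs 29.5% give about 0.763.
- f = 20%, c = 1/2: factor 0.900. Rates 54% vs 27% give 0.932; 45% vs 27% give 0.710, with the stopping probability up from 0.173 to 0.213.

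**7. Null.** With equal rates of 30%, the rejection probability is 0.0172 with the futility stop and 0.0248 without it. With both rates at 27% it is 0.0170 and 0.0249. Type I error is not inflated.

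**The case against.** **Exclusion 3 fits its group.** The drug-clearance rules (exclusions 1, 3 and 35) count from implant; the dose-stability rules (4 and 5) count from consent. This is a fair reading of why exclusion 3 is worded as it is. It does not make the look-back reach the baseline.

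**A drug-affected baseline is openly allowed.** Under 11.2.2 a subject may consent while still taking a biologic or targeted synthetic DMARD, with the baseline that day. This stands: the design tolerates some drug influence at baseline, and the fix below leaves that route untouched.

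**SAP 5.8.1 is a rescue rule.** It does not state that every assessment within 30 days of an injection is invalid. This also stands. It is used here only as the plan's own time scale.

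**Day 0 already provides an answer.** ACR20 from Day 0 is a key secondary endpoint. Day 0 is at least 14 days after implant, so an injection permitted by exclusion 3 lies more than 30 + 14 = 44 days before it. This is a real safeguard for interpretation, but under SAP 8.5 it is tested only if the primary succeeds. The baseline-timing sensitivity analysis (SAP 8.5.1) applies to the key secondaries, not to the primary.

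**The opiate rule has no exception for baseline.** A reader might infer that it does not apply to the consent visit. The text does not support that. A site may also ask about the last dose and book another day, and SAP 9.2 plans a sensitivity analysis for deviations that could affect the primary endpoint. What remains is the conflict over enforcement.

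**Other limits.** Entry requires at least 4 tender and 4 swollen joints at consent, which screens out the most suppressed candidates. Pain is one of five items, of which three are needed.

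**Conclusion.** The point holds at minor severity. Injection protection of the primary baseline is partial, falls by one day for each day between consent and implant, and is absent only at k = 30. A reader might infer that the baseline has no protection at all; at shorter gaps that is wrong. The opiate passages conflict over enforcement, not over coverage.

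A reader might also infer bias toward the device or an inflated type I error. The documents do not support this: both exposures precede randomization, so the expected effect is similar in the two arms, and the rejection probability under the null stays below 0.025. Nor is the stated power table wrong; it reproduces, and it does not address this source of dilution.

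The size is unknown because the documents give no frequency of recent injection or as-needed opiate use. The loss at the design assumption of 60% vs 30% is 0.004 to 0.027 (0.959 to 0.955-0.932). At 50% vs 30% it is about 0.01 to 0.06 (0.773 to 0.763-0.710). Both rest on the assumed 5-20% prevalence and one-third to one-half cut in response, equal in both arms.

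**What to change.** 1. Reconcile the reference date of exclusion 3 with the consent-day baseline, and reconcile Protocol 14.3 with 11.2.1 and 11.2.2. No particular window or clinical rule is proposed here.
2. In SAP 8.2.1, using the plan's own 30-day figure, treat a joint injected in the 30 days before consent as not evaluable at baseline. The existing rule then sets that joint to missing throughout and rescales the count.
3. Record any injection in the 30 days before consent, and the last as-needed opiate dose at the consent visit and at Week 12.
4. Before the primary dataset is locked, specify one sensitivity analysis of the primary ACR20 that either excludes subjects with an injection in the 30 days before consent or uses their Day 0 value as baseline. Note beside it that ACR20 from Day 0 for all subjects is already a key secondary.

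The cost is wording in both documents, one CRF item and one table. Depending on how exclusion 3 is reconciled, a few candidates may consent later. If enrollment is too advanced for eligibility wording to matter, steps 2 and 4 can still be specified before lock, as far as injection dates and joints can be retrieved from medication records.
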